17.7 MFIS Assessment

Because of my fatigue during the past 4 weeks...

	Never	Rarely	Sometimes	Often	Almost Always
1. I have been less alert.	0	1	2	3	4
2. I have had difficulty paying attention for long periods of time.	0	1	2	3	4
3. I have been unable to think clearly.	0	1	2	3	4
4. I have been clumsy and uncoordinated.	0	1	2	3	4
5. I have been forgetful.	0	1	2	3	4
6. I have had to pace myself in my physical activities.	0	1	2	3	4
7. I have been less motivated to do anything that requires physical effort.	0	1	2	3	4
8. I have been less motivated to participate in social activities.	0	1	2	3	4
9. I have been limited in my ability to do things away from home.	0	1	2	3	4
10. I have had trouble maintaining physical effort for long periods.	0	1	2	3	4
11. I have had difficulty making decisions.	0	1	2	3	4
12. I have been less motivated to do anything that requires thinking.	0	1	2	3	4
13. My muscles have felt weak.	0	1	2	3	4
14. I have been physically uncomfortable.	0	1	2	3	4
15. I have had trouble finishing tasks that require thinking.	0	1	2	3	4
16. I have had difficulty organizing my thoughts when doing things at home or at work.	0	1	2	3	4
17. I have been less able to complete tasks that require physical effort.	0	1	2	3	4
18. My thinking has been slowed down.	0	1	2	3	4
19. I have had trouble concentrating.	0	1	2	3	4
20. I have limited my physical activities.	0	1	2	3	4
21. I have needed to rest more often or for longer periods.	0	1	2	3	4

Physical Subscale	This scale can range from 0-36. It is computed by adding raw scores on the following items: 4+6+7+10+13+14+17+20+21.
Cognitive Subscale	This scale can range from 0-40. It is computed by adding raw scores on the following items: 1+2+3+5+11+12+15+16+18+19.
Psychosocial Subscale	This scale can range from 0-8. It is computed by adding raw scores on the following items: 8+9
Total MFIS Score	The total MFIS score can range from 0-84. It is computed by adding scores on the physical + cognitive + psychosocial subscales.

1. OVERVIEW

This Statistical Analysis Plan (SAP) describes the planned analysis and reporting for Horizon Pharma Ireland, Ltd. protocol HZNP-ACT-302 (Multicenter, Safety and Efficacy, Open-Label Extension Study of ACTIMMUNE® (interferon γ -1b) in Children and Young Adults with Friedreich's Ataxia), Final Version 2.0 incorporating Amendment 1, dated 28-SEP-2016.

The structure and content of this SAP provides sufficient detail to meet the requirements identified by the Food and Drug Administration (FDA), European Medicines Agency (EMA), and International Conference on Harmonization (ICH) of Technical Requirements for Registration of Pharmaceuticals for Human Use: Guidance on Statistical Principles in Clinical Trials [1]. All work planned and reported for this SAP will follow internationally accepted guidelines, published by the American Statistical Association [2] and the Royal Statistical Society [3], for statistical practice.

The planned analysis identified in this SAP may be included in clinical study reports (CSRs), regulatory submissions, or future manuscripts. Also, post-hoc exploratory analysis not necessarily identified in this SAP may be performed to further examine study data. Any post-hoc, or unplanned, exploratory analysis performed will be clearly identified as such in the final CSR.

In addition to the study protocol, the following documents were reviewed in preparation of this SAP:

- The electronic case report forms (eCRFs) for this Protocol
- ICH Guidance on Statistical Principles for Clinical Trials (E9).

The reader of this SAP is encouraged to also read the clinical protocol, and other identified documents, for details on the planned conduct of this study. Operational aspects related to collection and timing of planned clinical assessments are not repeated in this SAP unless relevant to the planned analysis.

2. STUDY OBJECTIVES AND ENDPOINTS

2.1 Study Objectives

2.1.1 Primary Objective

The primary objectives of this study are:

- To evaluate the long-term safety of ACTIMMUNE in subjects with Friedreich's Ataxia (FA).
- To evaluate the effect of ACTIMMUNE (interferon [IFN]- γ 1b) on the change from Baseline of HZNP-ACT-302 to Week 26 for all subjects and from Baseline of HZNP-ACT-301 to Week 26 of HZNP-ACT-302 (52-week treatment duration) for subjects receiving active treatment in both studies in neurological outcomes as measured by Friedreich's Ataxia Rating Scale (FARS) excluding the peripheral nervous system subscale score and the facial and tongue atrophy and fasciculations from the bulbar subscale score (FARS-mNeuro score).

2.1.2 Secondary Objectives

The secondary objectives of this study are to evaluate the effect of ACTIMMUNE (interferon [IFN]- γ 1b) on the change from Baseline(HZNP-ACT-302) to Week 26 for all subjects and from Baseline of HZNP-ACT-301 to Week 26 of HZNP-ACT-302 (52-week treatment duration) for subjects receiving active treatment in both studies for the following:

- Activities of Daily Living (ADL)
- The timed 25-foot-walk-test (T25FW)
- Responder rate (≥ 3 point improvement in the FARS-mNeuro score)
- Neurological outcome as measured by the total FARS score (FARStot)

2.2 Study Endpoints

The analysis for this study is for an abbreviated safety Clinical Study Report (CSR). All efficacy endpoints mentioned in the protocol have been removed and noted as changes to the planned analyses.

2.2.1 Safety Endpoints

Adverse event and concomitant medication data will be summarized. Clinical laboratory safety data, vital sign data, echocardiogram data, and ECG interval data will be summarized with descriptive statistics for Baseline of HZNP-ACT-302, post-dose, and change from Baseline of HZNP-ACT-302 to post-dose values. Shift tables will be presented for clinical laboratory values and ECG categorical results from Baseline of HZNP-ACT-302 to each post-dose visit. Physical examination findings will be listed by subject. Results of immunogenicity testing will be presented in tabular format.

[figure not shown]

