2.1 Schedule of Assessments

Study Phase	Visit #	Treatment Period				Follow-up Safety Visit
		Baseline ¹	1	2	3	
Week	1	4	13	26 (or PW)	28	
Study Days (\pm visit window)	Day 1 (Week 26 of Study HZNP-ACT-301)		29 (\pm 3) days	92 (\pm 3) days	183 (\pm 3) days	197 (\pm 3) days
Informed consent/assent	X					
Review of inclusion/exclusion criteria	X					
Weight/height, BSA ²	X	X	X	X		
Educate on dosing technique and schedule ³	X	X	X			
Dose given at study visit ⁴		X	X	X		
Dispense study drug ⁵	X	X	X			
Drug compliance		X	X	X		
Phone (email) contact for safety and dosing logistics ⁶	X	X	X			
Efficacy assessments ⁷						
Functional staging of FA ⁷	X		X	X		
FARS ⁷	X		X	X		
T25FW ⁷	X		X	X		
9-HPT ⁷	X		X	X		
Vision testing (LCSLC)	X				X	
Auditory testing (LiSN-S) ⁸	X				X	
Frataxin protein: whole blood, muscle biopsy (optional) ⁹ , and buccal cells	X		X	X		
Physician and Patient Global assessments	X		X	X		
ADL	X		X	X		
Quality of Life (QOL) Assessments						
PedsQL or SF-36 ¹⁰	X		X	X		
MFIS	X		X	X		
Safety Assessments						
TEAE, SAE assessment ¹¹	X	X	X	X	X	
Immunogenicity testing ¹²	X	X	X	X	X	
Echocardiogram	X				X	
ECG	X			X	X	
Physical examination ¹³	X	X ¹³	X	X	X ¹³	
Vital Signs: blood pressure, pulse, temperature	X	X	X	X	X	
Urine pregnancy test ¹⁴	X	X	X	X	X	
Prior/concomitant medications	X	X	X	X	X	X
Clinical laboratory evaluation ¹⁵ (hematology, chemistry, urinalysis)	X	X	X	X	X	
End treatment					X	

9-HPT=9-hole peg test, ADL=activities of daily living, BSA=body surface area, ECG=electrocardiogram, FA=Friedreich's Ataxia, FARS=Friedreich's Ataxia Rating Scale, IFN=interferon, LCSLC=Low-contrast Sloan letter chart, LiSN-S=Listening in Spatialized Noise-Sentences Auditory Test, MFIS=Modified Fatigue Impact Scale, PedsQL=Pediatric Quality of Life, PW=premature withdrawal, QOL=quality of life, SAE=serious adverse event, SF-36=36-item short form health survey, T25FW=timed 25-foot walk, TEAE=treatment-emergent adverse event.

Footnotes are presented on the next page.

- ¹ On Day 1 (Baseline), subjects will receive the last dose of assigned study drug (ACTIMMUNE or placebo) for HZNP-ACT-301, and undergo assessments; these assessments will serve as the Week 26 assessments for HZNP-ACT-301 and the Baseline assessments for HZNP-ACT-302.
- ² Height and weight will be measured at Baseline/Day 1 (Week 26 of Study HZNP-ACT-301), and Weeks 4, 13, and 26 to determine BSA; dosing will be based on BSA at Baseline/Day1, and Weeks 4 and 13.

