8. STUDY OBJECTIVES

8.1 Primary Study Objective

The primary objective is to evaluate the long-term safety of ACTIMMUNE (IFN- γ 1b) in subjects with FA.

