- ¹ On Day 1 (Baseline), subjects will receive the last dose of assigned study drug (ACTIMMUNE or placebo) for HZNP-ACT-301, and undergo assessments; these assessments will serve as the Week 26 assessments for HZNP-ACT-301 and the Baseline assessments for HZNP-ACT-302.
- ² Height and weight will be measured at Baseline/Day 1 (Week 26 of Study HZNP-ACT-301), and Weeks 4, 13, and 26 to determine BSA; dosing will be based on BSA at Baseline/Day1, and Weeks 4 and 13.
- ³ Study drug will be initiated at home following the Baseline/Day 1 visit at 10 $\mu\text{g}/\text{m}^2$ according to the subject's TIW dosing schedule. The planned dose escalation consists of two doses of ACTIMMUNE 10 $\mu\text{g}/\text{m}^2$ in the first week, followed by weekly escalation to 25, 50, and 100 $\mu\text{g}/\text{m}^2$ TIW on Days 8, 15, and 22, respectively; however, the dose may be reduced, interrupted, or held based on tolerability. All subjects are to be on a stable tolerated dose of study drug by Week 13 in order to continue study participation
- ⁴ At the Baseline/Day 1 visit (Week 26 of Study HZNP-ACT-301), subjects will receive the last dose of study drug from the double-blind Study HZNP-ACT-301 (ACTIMMUNE or placebo). The first dose for this open-label extension study (ACTIMMUNE 10 $\mu\text{g}/\text{m}^2$) will be administered at home before bedtime according to the subject's TIW dosing schedule. Dosing at Weeks 4, 13, and 26 will be performed at the clinic. All other doses will be administered at home before bedtime.
- ⁵ Subjects will be given a 4-week supply of study drug prior to clinic discharge at the Baseline/Day 1 Visit (Week 26 of Study HZNP-ACT-301). At the Week 4 and 13 Visits, subjects will be given a 6-week supply of study drug, and additional study drug will be directly shipped to the subjects' homes as needed; if direct shipment is not feasible, subjects may receive a full supply at Weeks 4 and 13 (9-week supply at Week 4 and 13-week supply at Week 13).
- ⁶ Subjects and/or caregivers will be contacted by email or phone to monitor safety and dosing logistics on a weekly basis during the dose-escalation period (from Day 1 through at least Week 4 [or later until a stable tolerated dose is reached]) and on a monthly basis after dose stabilization (from Week 4 or when dose is stabilized) through Week 26.
- ⁷ Functional staging, FARS, T25W, and 9-HPT will be performed at approximately the same time of day at each visit and by the same examiner.

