6.3 Derived and Computed Variables

The following derived and computed variables have been initially identified as important for the analyses of Safety, Efficacy and Exploratory endpoints. It is expected that additional variables may be required. The SAP will not be amended for additional variables that are not related to the primary target or key secondary target variables. Any additional derived or computed variables will be identified and documented in the SAS programs that create the analysis files. If the SAP is not amended, further derivations related to primary and secondary target variables will be described in the CSR.

- 302 Baseline = The last non-missing measurement/assessment on the date of Week 26 Visit from HZNP-ACT-301. If this measurement is missing or otherwise unavailable, it will be the last non-missing measurement/assessment on or prior to first dose in HZNP-

ACT-302.

- 301 Baseline = The last non-missing measurement/assessment prior to first dose of Study in HZNP-ACT-301.
- Study Day = Assessment Date – Date of Enrollment + 1
- Change from Baseline = Value at Post-Baseline – Value at Baseline
- Concomitant Medication is defined as any medication a subject has received concurrently with study treatment.
- Prior Medication is defined as any medication or therapies initiated prior to date of first dose of study drug. Medications that are started prior to the date of first dose of study drug and continue after the first dose of drug are considered to be both prior and concomitant medications.
- Treatment-Emergent Adverse Event (TEAE) – A TEAE is any adverse change from the subject's baseline condition that occurs on or after the date of the first dose of study drug through the duration of the clinical study.
- Related TEAE – Any TEAE with a reported relationship to study drug of 'possibly related'.
- Compliance = Calculated as the percentage of the number of vials used divided by the expected number of vials used, where the number of vials used is the number of used vials returned.

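### Safety changes and shifts are referenced only to the 302 Baseline, an on-drug visit for subjects given ACTIMMUNE in 301, so the legible plan leaves out whatever change arose during 301

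*SAP*

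**What the plan says.** The primary study objective in Protocol 8.1 reads "The primary objective is to evaluate the long-term safety of ACTIMMUNE", and SAP 2.1.1 repeats it.

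SAP 2.2.1 summarises laboratory, vital-sign, echocardiogram and ECG-interval data by "descriptive statistics for Baseline of HZNP-ACT-302, post-dose, and change from Baseline of HZNP-ACT-302 to post-dose values". For shifts it says: "Shift tables will be presented for clinical laboratory values and ECG categorical results from Baseline of HZNP-ACT-302 to each post-dose visit". No shift tables are planned for vital signs or echocardiograms.

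SAP 6.3 defines two baselines. One is "302 Baseline = The last non-missing measurement/assessment on the date of Week 26 Visit from HZNP-ACT-301", with a fallback to the last value on or before the first 302 dose. The other is "301 Baseline = The last non-missing measurement/assessment prior to first dose of Study in HZNP-ACT-301". The change formula is generic: "Change from Baseline = Value at Post-Baseline – Value at Baseline". SAP 9.2 to 9.4 do not say which baseline applies, so 2.2.1 governs.

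The footnotes to the SAP schedule (SAP 3) describe the visit: "On Day 1 (Baseline), subjects will receive the last dose of assigned study drug (ACTIMMUNE or placebo) for HZNP-ACT-301, and undergo assessments". Protocol 2.1 adds that "these assessments will serve as the Week 26 assessments for HZNP-ACT-301 and the Baseline assessments for HZNP-ACT-302".

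On display, the Statistical Analyses part of the Protocol Synopsis requires all summaries by 301 treatment and overall. SAP 6 says only that summaries are by overall treatment.

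**The concern.** For a subject who took placebo in 301, the 302 Baseline is a pre-drug value. For a subject who took ACTIMMUNE in 301, it is a value after 26 weeks of treatment. The same column heading therefore means two different things.

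The second kind of subject is the only one who reaches 52 weeks of exposure, and so carries most of the information on long-term safety. Suppose a transaminase, neutrophil, QTc or ejection-fraction change appeared during 301 and persisted. In the 302 change tables it is absorbed into the reference value. In a laboratory shift table it appears as abnormal at baseline and abnormal afterwards, which is not a shift.

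The 301 Baseline is the natural reference for a 52-week question, and the protocol uses it that way for efficacy (Protocol 9.6.1). The SAP then drops efficacy (2.2, 8 and 10). In its legible text, 301 baseline data survive only in demographic and efficacy-score tables (7.3). At stake is whether the study report can describe change over a year of treatment, or only change over the second half of it.

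**Working it through.** The documents give no sample size, effect size or error rate bearing on this point, so there is no stated figure to reproduce. The check is an identity with assumed inputs.

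**1. Is the 302 Baseline on-drug for the 301-active group?** Yes. It is the 301 Week 26 visit (SAP 6.3), entry requires 26 completed weeks of blinded treatment (Protocol 9.3.1), and the last blinded dose is given that day. In the order of procedures in Protocol 9.5.5.1, blood is drawn before that dose, while vital signs, echocardiogram and ECG follow it. The fallback in SAP 6.3 does not require a pre-drug value either.

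**2. What does the reference leave out?** For one subject:

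change from 301 Baseline = change during 301 + change from 302 Baseline.

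Set the 52-week drug-related change to 1 unit and let s be the share present at 301 Week 26 (assumed, 0 to 1). In subjects on ACTIMMUNE in both studies:

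| s | from 302 Baseline (1 − s) | from 301 Baseline |
|---|---|---|
| 0 | 1.00 | 1.00 |
| 0.25 | 0.75 | 1.00 |
| 0.50 | 0.50 | 1.00 |
| 0.75 | 0.25 | 1.00 |
| 0.90 | 0.10 | 1.00 |
| 1 | 0.00 | 1.00 |

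**3. Shift tables.** Assume 5% of this group are abnormal before any drug and 25% at 302 Week 26, with abnormalities persisting once present. From the 301 Baseline, new shifts are 25 − 5 = 20 points. From the 302 Baseline they depend on the proportion abnormal at 301 Week 26:

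- 25% abnormal: 25 − 25 = 0 points
- 15% abnormal: 25 − 15 = 10 points
- 5% abnormal: 25 − 5 = 20 points

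**4. Pooled tables.** Let w be the share of the Safety Population treated with ACTIMMUNE in 301. The randomisation ratio is not given, so w is assumed. If switchers from placebo show s after their first 26 weeks, the pooled mean change is w(1 − s) + (1 − w)s. At w = 1/2 it is 0.50 for every s. At w = 2/3 it runs from 0.67 (s = 0) to 0.33 (s = 1). A pooled mean therefore mixes first-exposure change with continued-exposure change.

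**5. Do other planned outputs supply the missing comparison?**

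- Absolute values: SAP 2.2.1 covers the 302 Baseline and post-dose values, so the pre-drug value is absent.
- Adverse events: Protocol 9.5.3.1.2 treats events ongoing from 301 as baseline signs or symptoms. An abnormality that arose in 301 and stays unchanged is therefore not treatment-emergent in 302.
- 301's own tables: these are not described here. Only 301 completers can enter 302, and subject-level shifts cannot be rebuilt from two separate marginal tables.

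**The case against.** The strongest reply is that the SAP does what the protocol asks. Protocol 9.1 makes 301 Week 26 the study Baseline, and Protocol 9.6.1 reserves the 52-week change for efficacy. Change in the first 26 weeks belongs to 301, which had a placebo arm. This explains the choice, but it does not give the study a 52-week safety comparison.

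A second reply is that abnormalities are not hidden. Absolute laboratory, vital-sign and ECG values by visit, counts below, within and above range, ECG categories, and listings with out-of-range laboratory values flagged are all planned (SAP 9.2 to 9.4). A persistent laboratory abnormality would be visible as out of range at each visit. This stands as partial mitigation: it shows the level, but not the change from before drug.

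A third reply is that a 52-week change without a control mixes drug effect with the course of a progressive disease that includes cardiomyopathy (Protocol 7.1). This also stands, and limits how the added tables may be read.

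Two further inferences should be resisted.

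- A reader might infer that re-titration from the lowest dose will make continuing subjects look improved. The first post-baseline laboratory sample is at Day 29 (± 3), after planned escalation to the top level on Day 22, so this is weak.
- A reader might treat the pooled dilution in step 4 as part of the baseline problem. It comes mainly from pooling, and following the protocol's display by 301 treatment largely cures it. That display does not make the reference value pre-drug.

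**Conclusion.** The point holds as a reporting gap, not a numerical error. In the legible SAP, every safety change and shift is referenced to a visit that is on-drug for 301-active subjects. No planned safety table gives the change from pre-drug to 302 Week 26 in the only group with 52 weeks of exposure. What is omitted is exactly the share s that arose in 301.

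A reader might go further and infer that this group must show about zero change by construction. The documents do not support that. It requires an effect that had plateaued by 301 Week 26 and then persisted (s near 1), and no data on this are given. A late or cumulative effect (s near 0) would still show in full.

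Two limits apply. The list of planned tables in SAP 13 cannot be read, so the statement rests on the SAP's legible text. The values of s and w, and the rates in step 3, are assumptions used to show the range. The change is worth making because it serves the primary objective at small cost.

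**What to change.** In SAP 2.2.1 and 9.2 to 9.4, for subjects on ACTIMMUNE in both studies, add the following from the 301 Baseline of SAP 6.3 to each 302 visit at which the parameter is measured:

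- change tables for laboratory values, vital signs and ECG intervals, and for echocardiogram measures where a 301 value exists;
- shift tables for laboratory values and ECG category.

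Present safety tables by 301 treatment as well as overall, as the Protocol Synopsis requires. Name the baseline in each table title, and label the 302-Baseline tables as incremental change. State in the report that the 52-week change is uncontrolled and combines any drug effect with disease progression.

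The cost is SAP wording, one extra set of tables, and merging 301 baseline safety records. SAP 7.3 already draws on 301 data, but it does not name laboratory, vital-sign, ECG or echocardiogram records. Some parameters may lack a 301 Baseline. Echocardiography in particular was added to 302 by amendment, and whether 301 has a baseline echocardiogram cannot be told from these documents. No new assessments are needed.

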3. OVERALL STUDY DESIGN AND PLAN

This is a multi-center, dose-escalation, open-label extension study of HZNP-ACT-301 examining the safety and efficacy of ACTIMMUNE in the treatment of FA in children and young adults. Subjects who complete 26 weeks of blinded treatment in HZNP-ACT-301 will be eligible for enrollment in this study. In order to maintain the study blind in HZNP-ACT-301, all subjects in the open-label extension study will undergo ACTIMMUNE titration, regardless of treatment received in HZNP-ACT-301. The sample size is not based on statistical considerations.

The overall maximum treatment duration for an individual subject is expected to be 26 weeks, with a Follow-Up Safety Visit two weeks following last dose of study drug. As per the study design and schedule of events below ([Table 1](#), [Table 2](#)), subjects will all be assigned to start on ACTIMMUNE 10 $\mu\text{g}/\text{m}^2$ in the first week. This will be followed by weekly escalation to 25, 50, and 100 $\mu\text{g}/\text{m}^2$ three times a week (TIW) on Days 8, 15, and 22, respectively. The study drug dose is planned to be escalated on a weekly basis over the first 4 weeks of treatment (from 10 $\mu\text{g}/\text{m}^2$ to 100 $\mu\text{g}/\text{m}^2$), however, the dose may be reduced, interrupted, or held based on tolerability. By Week 13, all subjects are to be on a stable tolerated dose of study drug in order to continue study participation.

Table 1. Study Design

Schematic of Study Design

¹ Week 26 of HZNP-ACT-301 will serve as the Baseline Visit (Day 1) for this study. Subjects will receive the last dose of the randomized drug from HZNP-ACT-301 in a double-blind fashion, and the first dose of study drug for the open-label extension study (10 $\mu\text{g}/\text{m}^2$) will be distributed for administration at home according to the planned TIW dosing schedule.

² The planned dose escalation consists of two doses of ACTIMMUNE 10 $\mu\text{g}/\text{m}^2$ in the first week, followed by weekly escalation to 25, 50, and 100 $\mu\text{g}/\text{m}^2$ TIW on Days 8, 15, and 22, respectively; however, the dose may be reduced, interrupted, or held based on tolerability. All subjects are to be on a stable tolerated dose of study drug by Week 13 in order to continue study participation.

³ Subjects and/or caregivers will be contacted by email or phone to monitor safety and dosing logistics on a weekly basis from Day 1 (Week 26 of HZNP-ACT-301) through Week 4 (or until stable tolerated dose is achieved) and on a monthly basis after Week 4 (or after dose stabilization) through Week 26.

Table 2. Schedule of Events

Study Phase	Visit #	Treatment Period			Follow-up Safety Visit
		Baseline ¹	1	2	
		Week	1	4	28
Study Days (\pm visit window)	Day 1 (Week 26 of Study HZNP-ACT-301)		29 (\pm 3) days	92 (\pm 3) days	183 (\pm 3) days
Informed consent/assent	X				
Review of inclusion/exclusion criteria	X				
Weight/height, BSA ²	X	X	X	X	
Educate on dosing technique and schedule ³	X	X	X	X	
Dose given at study visit ⁴		X	X	X	X
Dispense study drug ⁵	X	X	X	X	
Drug compliance		X	X	X	X
Phone (email) contact for safety and dosing logistics ⁶	X	X	X	X	
Efficacy assessments ⁷					
Functional staging of FA ⁸	X		X	X	
FARS ⁹	X		X	X	
T25FW ¹⁰	X		X	X	
9-HPT ¹¹	X		X	X	
Vision testing (LCSLC)	X				X
Auditory testing (LiSN-S) ¹²	X				X
Frataxin protein: whole blood, muscle biopsy (optional) ¹³ , and buccal cells	X		X	X	
Physician and Patient Global assessments	X		X	X	
ADL	X		X	X	
Quality of Life (QOL) Assessments					
PedsQL or SF-36 ¹⁴	X		X	X	
MFIS	X		X	X	
Safety Assessments					
TEAE, SAE assessment ¹⁵	X	X	X	X	X
Immunogenicity testing ¹⁶	X	X	X	X	X
Echocardiogram	X				X
ECG	X		X	X	
Physical examination ¹⁷	X	X ¹⁸	X	X	X ¹⁹
Vital Signs: blood pressure, pulse, temperature	X	X	X	X	
Urine pregnancy test ²⁰	X	X	X	X	
Prior/concomitant medications	X	X	X	X	X
Clinical laboratory evaluation ²¹ (hematology, chemistry, urinalysis)	X	X	X	X	
End treatment					X

9-HPT=9-hole peg test, ADL=activities of daily living, BSA=body surface area, ECG=electrocardiogram, FA=Friedreich's Ataxia, FARS=Friedreich's Ataxia Rating Scale, IFN=interferon, LCSLC=Low-contrast Sloan letter chart, LiSN-S=Listening in Spatialized Noise-Sentences Auditory Test, MFIS=Modified Fatigue Impact Scale, PedsQL=Pediatric Quality of Life, PW=premature withdrawal, QOL=quality of life, SAE=serious adverse event, SF-36=36-item short form health survey, T25FW=timed 25-foot walk, TEAE=treatment-emergent adverse event.

Footnotes are presented on the next page.

- ¹ On Day 1 (Baseline), subjects will receive the last dose of assigned study drug (ACTIMMUNE or placebo) for HZNP-ACT-301, and undergo assessments; these assessments will serve as the Week 26 assessments for HZNP-ACT-301 and the Baseline assessments for HZNP-ACT-302.
- ² Height and weight will be measured at Baseline/Day 1 (Week 26 of Study HZNP-ACT-301), and Weeks 4, 13, and 26 to determine BSA; dosing will be based on BSA at Baseline/Day1, and Weeks 4 and 13.
- ³ Study drug will be initiated at home following the Baseline/Day 1 visit at 10 $\mu\text{g}/\text{m}^2$ according to the subject's TIW dosing schedule. The planned dose escalation consists of two doses of ACTIMMUNE 10 $\mu\text{g}/\text{m}^2$ in the first week, followed by weekly escalation to 25, 50, and 100 $\mu\text{g}/\text{m}^2$ TIW on Days 8, 15, and 22, respectively; however, the dose may be reduced, interrupted, or held based on tolerability. All subjects are to be on a stable tolerated dose of study drug by Week 13 in order to continue study participation
- ⁴ At the Baseline/Day 1 visit (Week 26 of Study HZNP-ACT-301), subjects will receive the last dose of study drug from the double-blind Study HZNP-ACT-301 (ACTIMMUNE or placebo). The first dose for this open-label extension study (ACTIMMUNE 10 $\mu\text{g}/\text{m}^2$) will be administered at home before bedtime according to the subject's TIW dosing schedule. Dosing at Weeks 4, 13, and 26 will be performed at the clinic. All other doses will be administered at home before bedtime.
- ⁵ Subjects will be given a 4-week supply of study drug prior to clinic discharge at the Baseline/Day 1 Visit (Week 26 of Study HZNP-ACT-301). At the Week 4 and 13 Visits, subjects will be given a 6-week supply of study drug, and additional study drug will be directly shipped to the subjects' homes as needed; if direct shipment is not feasible, subjects may receive a full supply at Weeks 4 and 13 (9-week supply at Week 4 and 13-week supply at Week 13).
- ⁶ Subjects and/or caregivers will be contacted by email or phone to monitor safety and dosing logistics on a weekly basis during the dose-escalation period (from Day 1 through at least Week 4 [or later until a stable tolerated dose is reached]) and on a monthly basis after dose stabilization (from Week 4 or when dose is stabilized) through Week 26.
- ⁷ Functional staging, FARS, T25W, and 9-HPT will be performed at approximately the same time of day at each visit and by the same examiner.
- ⁸ The LiSN-S will only be performed for subjects who had a normal audiogram prior to enrollment in HZNP-ACT-301. The LiSN-S will be performed at the Baseline/Day 1 (Week 26 of Study HZNP-ACT-301) and Week 26 visits.
- ⁹ Muscle biopsies will be optional for each subject, and consent will be signed prior to biopsy collection. Biopsies will be the last efficacy assessment of the day at Weeks 13 and 26.
- ¹⁰ The PedsQL (study subject and parent/caregiver assessments) will be administered throughout the study for subjects who received the PedsQL at their Baseline Visit of the HZNP-ACT-301 study (even if subjects turn 18 during their participation in either Study HZNP-ACT-301 or HZNP-ACT-302). The SF-36 will continue to be administered throughout the study for subjects who completed the SF-36 during their HZNP-ACT-301 study participation.
- ¹¹ Adverse events occurring or worsening on or after the date of administration of the first dose of study drug at home through the end of the study will be considered treatment-emergent adverse events (TEAEs). All SAEs that occur on or after the date of administration of the first dose of study drug at home through two weeks after study discontinuation will be recorded.
- ¹² If a subject tests positive for anti-drug antibodies (ADA), he/she will be followed until ADA levels revert to baseline.
- ¹³ Brief physical examinations will be performed at the Week 4 and Follow-Up Safety Visits; all other examinations will be complete physical examinations.
- ¹⁴ Only for female subjects of childbearing potential.
- ¹⁵ Collect blood samples for clinical safety laboratory testing (9.3 mL; 1.0 mL for hematology, 3.5 mL for chemistry, 3.0 mL discard, and 1.8 mL for PT/INR/aPTT) and a urine sample for urinalysis.

